## **2. STUDY OBJECTIVES AND ENDPOINTS**

### **2.1. Study Objectives**

#### **2.1.1. Primary Objective**

- To assess the efficacy of INCB050465 in terms of ORR in subjects with relapsed or refractory DLBCL in Group A.

#### **2.1.2. Secondary Objectives**

- To assess the duration of response (DOR) in Group A.
- To assess progression-free survival (PFS) in Group A.
- To assess OS in Group A.
- To characterize the safety of INCB050465 in Group A and Group B.

### **2.2. Study Endpoints**

#### **2.2.1. Primary Endpoint**

- Objective response rate in Group A, defined as the percentage of subjects with a CR/CMR or PR/PMR as defined by revised response criteria for lymphomas ([Cheson et al 2014](#)), as determined by an Independent Review Committee (IRC).

#### **2.2.2. Secondary Endpoints**

- Duration of response in Group A, defined as the time from first documented evidence of CR/CMR or PR/PMR until disease progression or death from any cause among subjects who achieve an objective response, as determined by radiographic disease assessment provided by an IRC.
- Progression-free survival in Group A, defined as the time from the date of the first dose of study drug until the earliest date of disease progression, as determined by radiographic disease assessment provided by an IRC, or death from any cause.
- OS in Group A, defined as the time from the date of the first dose of study drug until death by any cause.

- Safety as measured by clinical assessments, including vital signs and physical examinations, 12-lead electrocardiograms (ECG), chemistry and hematology laboratory values, and AEs.

### 3. SUBJECT ELIGIBILITY

Deviations from eligibility criteria are not allowed because they can potentially jeopardize the scientific integrity of the study, regulatory acceptability, and/or subject safety. Therefore, adherence to the criteria as specified in the Protocol is essential.

#### 3.1. Subject Inclusion Criteria

A subject who meets all of the following criteria may be included in the study:

1. Men and women, aged 18 years or older (except in South Korea, aged 19 or older).
2. Relapsed or refractory DLBCL, which has been histologically documented, defined as having received at least 2 but no more than 5 prior treatment regimens (eg, an anti-CD20 antibody, an anti-CD20 antibody with or without chemotherapy, or chemotherapy alone) and ineligible for HDC/ASCT.
3. Group B only: Must have received prior Bruton's tyrosine kinase (BTK) inhibitor therapy (eg, ibrutinib).
4. Subjects must be willing to undergo an incisional or excisional lymph node biopsy of accessible adenopathy or provide the most recent, available archived tumor biopsy.
5. Must have  $\geq 1$  measurable nodal lesion ( $\geq 2$  cm in longest dimension) or  $\geq 1$  measurable extranodal lesion ( $> 1$  cm in longest dimension) on computed tomography (CT) scan or magnetic resonance imaging (MRI).
6. ECOG performance status 0 to 2 (see [Table 10](#)).
7. Adequate hematologic, hepatic, and renal function (values must not be achieved with growth factors):
  - a. Absolute neutrophil count (ANC)  $\geq 1.0 \times 10^9/L$ .
  - b. Hemoglobin  $\geq 8.0$  g/dL.
  - c. Platelet count  $\geq 50 \times 10^9/L$ .
  - d. Total bilirubin  $\leq 1.5 \times$  upper limit of normal (ULN).

- e. Alanine aminotransferase (ALT)/aspartate aminotransferase (AST)  $\leq 3.0 \times \text{ULN}$  or  $\leq 5 \times \text{ULN}$  in the presence of liver metastases.
  - f. Calculated creatinine clearance  $\geq 50 \text{ mL/min}$  by the Cockcroft-Gault Equation or the estimated glomerular filtration rate  $\geq 50 \text{ mL/min/1.73 m}^2$  using the Modification of Diet in Renal Disease formula.
8. Willingness to avoid pregnancy or fathering children based on the criteria below:
- a. Woman of nonchildbearing potential (ie, surgically sterile with a hysterectomy and/or bilateral oophorectomy OR  $\geq 12$  months of amenorrhea and at least 55 years of age).
  - b. Woman of childbearing potential who has a negative serum pregnancy test at screening and who agrees to take appropriate precautions to avoid pregnancy (with at least 99% certainty) from screening through safety follow-up. Permitted methods that are at least 99% effective in preventing pregnancy (see [Appendix A](#)) should be communicated to the subject and their understanding confirmed.
  - c. Man who agrees to take appropriate precautions to avoid fathering children (with at least 99% certainty) from screening through at least 93 days after the last dose of study treatment. Permitted methods that are at least 99% effective in preventing pregnancy (see [Appendix A](#)) should be communicated to the subject and their understanding confirmed.
9. Ability to comprehend and willingness to sign an informed consent form (ICF).

### 3.2. Subject Exclusion Criteria

A subject who meets any of the following criteria will be excluded from the study:

1. Primary mediastinal (thymic) large B-cell lymphoma.
2. Known brain or central nervous system metastases or history of uncontrolled seizures.
3. Allogeneic stem cell transplant within the last 6 months, or active graft versus host disease following allogeneic transplant, or autologous stem cell transplant within the last 3 months before the date of the first dose of study drug.
4. Use of immunosuppressive therapy within 28 days of the date of study drug administration. Immunosuppressive therapy includes, but is not limited to, cyclosporine A, tacrolimus, or high-dose corticosteroids. Subjects receiving corticosteroids must be at a dose level  $\leq 10 \text{ mg/day}$  within 7 days of study drug administration.
5. Prior treatment with the following:
  - a. Group A: Prior treatment with a selective PI3K $\delta$  inhibitor (eg, idelalisib), a pan-PI3K inhibitor, or a BTK inhibitor (eg, ibrutinib).
  - b. Group B: Prior treatment with a selective PI3K $\delta$  inhibitor (eg, idelalisib) or a pan-PI3K inhibitor.

6. Receipt of anticancer medications or investigational drugs within the following intervals before the date of the first dose of study drug:
  - a. < 10 weeks from completion of any radio- or toxin-immunoconjugates.
  - b. < 6 weeks for mitomycin-C or nitrosoureas.
  - c. < 4 weeks for immunotherapy.
  - d. < 3 weeks for radiotherapy.
  - e. < 2 weeks for any investigational agent or other anticancer medications.
7. Prior treatment-related toxicities that have not resolved to  $\leq$  Grade 1 before the date of study drug administration date except for stable chronic toxicities ( $\leq$  Grade 2) not expected to resolve (eg, stable Grade 2 peripheral neurotoxicity).
8. Concurrent anticancer therapy (eg, chemotherapy, radiation therapy, surgery, immunotherapy, biologic therapy, hormonal therapy, investigational therapy, or tumor embolization).
9. Use or expected use during the study of any prohibited medications, including potent cytochrome P450 (CYP) 3A4 inhibitors or inducers (see [Appendix B](#)) within 14 days or 5 half-lives (whichever is longer) before the date of study drug administration.
10. Significant concurrent, uncontrolled medical condition including, but not limited to, renal, hepatic, hematological, gastrointestinal, endocrine, pulmonary, neurological, cerebral, or psychiatric disease.
11. Current or previous other malignancy within 3 years of study entry, except cured basal or squamous cell skin cancer, superficial bladder cancer, prostate intraepithelial neoplasm, carcinoma *in situ* of the cervix, or other noninvasive or indolent malignancy without sponsor approval.
12. History of stroke or intracranial hemorrhage within 6 months of the date of study drug administration.
13. Chronic or current active infectious disease requiring systemic antibiotics, antifungal, or antiviral treatment, and exposure to a live vaccine within 30 days of study drug administration.
14. Known human immunodeficiency virus (HIV) infection or positivity on immunoassay.  
Note: HIV screening test is optional for subjects enrolled in the United States, but subjects with known HIV infection enrolled in the United States will be excluded.
15. Liver disease:
  - a. Evidence of hepatitis B virus (HBV) or hepatitis C virus (HCV) infection or risk of reactivation: HBV DNA and HCV RNA must be undetectable. Subjects cannot be positive for hepatitis B surface antigen (HBsAg) or anti-hepatitis B core antibody. Subjects who have positive anti-HBs as the only evidence of prior exposure may participate in the study provided that there is both 1) no known history of HBV infection, and 2) verified receipt of hepatitis B vaccine.
16. Clinically significant cardiac disease, including unstable angina, acute myocardial infarction, and or cardiac conduction issues within 6 months of the date of study drug administration.

17. Current New York Heart Association Class II to IV congestive heart failure or uncontrolled arrhythmia.
18. Presence of an abnormal ECG that is clinically meaningful. Screening QTc interval > 450 milliseconds is excluded (corrected by Fridericia). In the event that a single QTc is > 450 milliseconds, the subject may enroll if the average QTc for 3 ECGs is < 450 milliseconds.
19. Unable to swallow oral medication, malabsorption syndrome, disease significantly affecting gastrointestinal function, total resection of the stomach or small bowel, ulcerative colitis, symptomatic inflammatory bowel disease, or partial or complete bowel obstruction.
20. Known hypersensitivity or severe reaction to INCB050465 or its excipients (INCB050465 IB).
21. Currently pregnant or breastfeeding.
22. Any condition that would, in the investigator's judgment, interfere with full participation in the study, including administration of study drug and attending required study visits; pose a significant risk to the subject; or interfere with interpretation of study data.

## 4. INVESTIGATIONAL PLAN

### 4.1. Overall Study Design

This is a Phase 2, multicenter, international, open-label study designed to evaluate the safety and efficacy of INCB050465 20 mg QD for 8 weeks followed by 20 mg once weekly. The study drug will be administered orally to subjects with relapsed or refractory DLBCL (see [Figure 1](#)). The study consists of 2 groups: Group A and Group B. In Group A, 100 subjects who were not previously treated with a BTK inhibitor (eg, ibrutinib) will be enrolled. In Group B, up to 20 subjects who were previously treated a BTK inhibitor (eg, ibrutinib) will be enrolled. Subjects will be evaluated for ORR by an independent review committee (IRC) and followed for DOR, PFS, and OS. Subjects may receive treatment until disease progression, death, unacceptable toxicity, or consent withdrawal. An interim futility analysis is planned when the first 40 subjects in Group A have been treated and have been evaluated for response or have permanently discontinued study treatment because of disease progression, withdrawal of consent, or death. Group A of the study will be terminated for futility if  $\leq 13$  of the 40 subjects have responded (ie, CR/CMR or PR/PMR) based on assessments provided by the IRC; otherwise the study will continue. A timely assessment of response will be performed to avoid the risk of overenrollment. No formal futility analysis will be conducted for Group B.

[figure not shown]
Subjects who have relapsed or refractory, histologically confirmed DLBCL will be screened for eligibility. Those who meet the eligibility criteria will be administered study drug (see [Section 5.2](#)). Subjects will be monitored for safety and efficacy periodically until disease progression, death, unacceptable toxicity, or withdrawal of informed consent. An independent Data Monitoring Committee (IDMC) will review safety data periodically as stated in the IDMC charter.

After treatment discontinuation, subjects will be followed for safety and survival. Subjects who have discontinued study treatment due to reasons other than disease progression will be followed for either radiologic disease progression, the start of a new anticancer therapy, or death, whichever comes first. The study will be closed no later than 2 years after the first dose of INCB050465 is administered to the last patient enrolled, at which point an analysis of OS will be conducted.

**Note:** With Amendment 4, Protocol-required procedures have been reduced for ongoing subjects.

**Figure 1: Study Design**

## 4.2. Measures Taken to Avoid Bias

This is an open-label study; no comparisons will be made between subjects or against historical controls. Measurements of safety and efficacy are objective measurements, and only comparisons to pretreatment conditions will be made. Safety will be objectively assessed using NCI CTCAE v4.03 (NCI 2009) guidelines; response will be assessed by an IRC using the Lugano classification (Cheson et al 2014).

## 4.3. Number of Subjects

### 4.3.1. Planned Number of Subjects and Sites

The study will enroll 100 to 120 subjects across approximately 80 sites.

### 4.3.2. Replacement of Subjects

No subjects will be replaced at any time during this study.

## 4.4. Duration of Treatment and Subject Participation

After signing the ICF, screening assessments may be completed over a period of up to 28 days. Each subject enrolled in the study may continue to receive study treatment in continuous 21-day

intervals. If the subject discontinues INCB050465, the treatment period will end, and the subject will enter the 30-day safety follow-up period after which the subject will enter the survival follow-up period (see Section 6.4). Study participation, excluding survival follow-up, is expected to average approximately 11 months per subject. Survival follow-up may average approximately 12 months.

#### **4.5. Overall Study Duration**

The study begins when the first subject signs the ICF. It is estimated that the study will take approximately 1.5 years to accrue 120 subjects and that the study will be closed no later than 2 years after the first dose of INCB050465 is administered to the last subject enrolled.

#### **4.6. Study Termination**

The investigator retains the right to terminate study participation at any time, according to the terms specified in the study contract. The investigator is to notify the institutional review board (IRB)/independent ethics committee (IEC) in writing of the study's completion or early termination, send a copy of the notification to the sponsor or sponsor's designee, and retain 1 copy for the site study regulatory file.

The sponsor may terminate the study electively or do so if required by a regulatory agency or upon advice from the IDMC. If the study is terminated prematurely, then the sponsor will notify the investigators, the IRBs and IECs, and regulatory bodies of the decision and reason for termination of the study. The IDMC will recommend termination of the study if warranted, as described in the IDMC charter.

Upon study closure, subjects who are still receiving study treatment will have the option to transition to Study INCB 50465-214, in which they may continue to receive study treatment.

### **5. TREATMENT**

#### **5.1. Treatment Assignment**

##### **5.1.1. Subject Numbering and Treatment Assignment**

Study sites will enter subject demographic and baseline data into the interactive web response system (IWRS) to receive a subject number and treatment allocation.

All subject numbers will be 6 digits; the first 3 digits will be the site number, and the last 3 digits will be the subject's number. This subject number will be maintained throughout the study and will not be reassigned. Subjects who withdraw consent or discontinue from the study after being assigned a subject number will retain their initial number.

Site staff will contact the IWRS to allocate the subject to treatment assignment and obtain the initial study drug assignment. The investigator or designee will select the assigned bottles of study drug from their stock that correspond to the number provided by the IWRS and dispense the study drug to the subject. All subsequent dispensing of study drug should follow this process. Refer to the IWRS manual for detailed information.

If a subject is mistakenly given a bottle of study drug that is not the bottle assigned by the IWRS, the IWRS help desk must be notified immediately. The reason for the misallocation of the study drug must be documented by the study site and reported to the IRB/IEC.

For subjects who signed an ICF but are not allocated study drug and for subjects who are allocated study drug but were not treated, refer to the electronic case report form (eCRF) Completion Guidelines for instruction on which eCRFs to complete.

### 5.1.2. Randomization and Blinding

Not applicable.

## 5.2. INCB050465

### 5.2.1. Description and Administration

The dose and regimen of INCB050465 is 20 mg QD for 8 weeks followed by 20 mg once weekly. INCB050465 will be taken orally with water in a fasted state except on mornings of [REDACTED] clinic visits (see Table 11). Subjects should refrain from food consumption for 2 hours before and 1 hour after administration of INCB050465. The dosage strengths and form are 5 mg and 20 mg tablets (see Table 1).

**Table 1: Description and Administration**

Compound name	INCB050465
Dosage Strengths	5 mg and 20 mg
Form	Tablet
Active compound	INCB050465
Route of administration	Oral
Dose and Regimen	20 mg QD for 8 weeks followed by 20 mg once weekly
Instructions	INCB050465 will be taken orally with water in a fasted state except on mornings of [REDACTED] clinic visits (see Table 11). Subjects should refrain from food consumption for 2 hours before and 1 hour after administration of INCB050465.

### 5.2.2. Supply, Packaging, and Labeling

INCB050465 will be provided as 5-mg and 20-mg tablets packaged in high-density polyethylene bottles. No preparation is required.

All Incyte investigational product labels will be in the local language and will comply with the legal requirements of each country.

*Pneumocystis jirovecii* pneumonia prophylaxis is required as coadministration with INCB050465; the prophylactic agents will be provided by Incyte. Incyte will determine the most appropriate manner in which to supply a prophylactic agent per country based on regulatory considerations. Further details are available in the study pharmacy manual.

### **5.2.3. Storage**

Bottles of INCB050465 tablets should be stored at ambient conditions (15°C-30°C or 59°F-86°F).

### **5.2.4. Instruction to Subjects for Handling INCB050465**

The subject must be instructed in the handling of study drug as follows:

- To store study drug at room temperature.
- To remove from the study drug bottle only the number of tablets needed at the time of administration.
- Not to remove doses in advance of the next scheduled administration.
- To make every effort to take doses on schedule.
- To report any missed doses.
- To keep INCB050465 in a safe place and out of reach of children.
- To bring all used and unused study drug kits to the site at each visit.

## **5.3. Treatment Compliance**

Compliance with all study-related treatments should be emphasized to the subject by the site personnel, and appropriate steps should be taken to optimize compliance during the study. Compliance with INCB040465 will be calculated by the sponsor based on the drug accountability documented by the site staff and monitored by the sponsor/designee (tablet counts). Subjects will be instructed to bring all study drugs with them to the study visits for site personnel to conduct tablet counts to assess study drug accountability. The drug accountability documentation will be used by the sponsor to calculate treatment compliance.

## **5.4. Treatment Interruptions and Adjustments**

### **5.4.1. Criteria and Procedures for Dose Interruptions and Reductions of INCB050465**

Treatment with INCB050465 may be interrupted for up to 14 days to allow for resolution of toxicity. Subjects may resume treatment if no medical condition or other circumstance exists that, in the opinion of the investigator, would make the subject unsuitable for further participation in the study. The treating investigator should contact the sponsor to discuss the case of any subject whose treatment has been interrupted for more than 14 days before restarting treatment with INCB050465.

Because subjects may enter the study with extensive pretreatment and/or severe bone marrow infiltration by the primary disease, guidelines for dose interruption for hematologic AEs (see [Table 2](#)) are provided. The starting dose and dose reduction levels of INCB050465 are provided (see [Table 3](#)). Individual decisions regarding dose interruption and reduction should be made using clinical judgment and in consultation with the sponsor's medical monitor, taking into account relatedness of the AE to the study drug and the subject's underlying condition. Adverse events that have a clear alternative explanation or transient ( $\leq 72$  hours) abnormal laboratory values without associated clinically significant signs or symptoms may be exempt from dose-reduction guidelines.

**Table 2: Guidelines for Interruption and Restarting Study Drug**

ADVERSE EVENT	ACTION TAKEN
Chemistry	

 
• AST and/or ALT is Grade 3 (<math>> 5.0 \times \text{ULN}</math>).
 
 
Note: In subjects with liver metastasis-related elevations at baseline, contact sponsor to discuss clinical management and possible dose reductions.
	
Step 1: Interrupt INCB050465 and monitor weekly until the toxicity has resolved to <math>\leq</math> Grade 1.
 
Step 2: Restart INCB050465 at next lower dose with medical monitor approval. Monitor as clinically indicated.

Hematology	

 
• Grade 3 ANC (<math>< 1.0 \times 10^9/\text{L}</math>).
 
• Platelet count is Grade 2 (50 to <math>< 75 \times 10^9/\text{L}</math>) for subjects who enrolled with platelets <math>> 100 \times 10^9/\text{L}</math>.
 
• Platelet count is Grade 3 (<math>< 50 \times 10^9/\text{L}</math>) for subjects who enrolled with platelets <math>\leq 100 \times 10^9/\text{L}</math>.
 
	
Step 1: Interrupt INCB050465 up to 14 days until the toxicity has resolved to <math>\leq</math> Grade 1 or pretherapy baseline. For Grade 3 ANC, monitor at least weekly.
 
Step 2: Restart INCB050465 at same dose; monitor as clinically indicated.

 
• Grade 4 ANC (<math>< 0.5 \times 10^9/\text{L}</math>).
 
• Grade 3 or Grade 4 ANC with an oral temperature of at least <math>38.5^\circ\text{C}</math> OR with <math>\geq</math> Grade 3 infection.
 
• Platelet count is Grade 4 (<math>< 25 \times 10^9/\text{L}</math>).
 
	
Step 1: Interrupt INCB050465 up to 14 days until the toxicity has resolved <math>\leq</math> Grade 1. (For Grade 4 ANC, monitor ANC at least weekly.)
 
Step 2: Restart INCB050465 at same dose. If assessed as related to INCB050465, restart at next lower dose. Monitor as clinically indicated.

Other toxicities	

 
• Diarrhea/colitis (Grade 1)
 
	
Step 1: Treat with antimotility agents (eg, 4 mg loperamide followed by 2 mg every 4 hours or after every unformed stool) and initiate supportive care (see Section 5.4.2). If not improved after 48 hours, treat per guidance for Grade <math>\geq 2</math>.


 
• Diarrhea/colitis (Grade <math>\geq 2</math>)
 
	
Step 1: Interrupt INCB050465. Perform work-up for infection (including CMV, C. difficile, etc). Initiate or continue supportive care (see Section 5.4.2). Consider colonoscopy with biopsy for Grade <math>\geq 3</math>.
 
Step 2: If infection is ruled out, start oral steroids, or consider IV steroids if subject is being given IV fluids. If no improvement with oral steroids, switch to IV steroids.
 
When diarrhea resolves to Grade <math>\leq 1</math>, continue supportive care and taper steroids over 4 weeks. When taper is complete and diarrhea is Grade <math>\leq 1</math>, restart INCB050465 at next lower dose with approval of the medical monitor.
 
If Grade <math>\geq 2</math> diarrhea reoccurs, permanently discontinue INCB050465.

 
• Pneumonitis (Grade 1)
 
	
Step 1: Interrupt INCB050465 until the toxicity has resolved.
 
Step 2: Restart INCB050465 at next lower dose. Monitor as clinically indicated.

 
• Pneumonitis (Grade <math>\geq 2</math>)
 
	
Permanently discontinue INCB050465.

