**Table 2: Guidelines for Interruption and Restarting Study Drug (Continued)**

ADVERSE EVENT	ACTION TAKEN

 
• Skin toxicity (eg, rash, pruritus, etc, unless otherwise specified) (Grade 2-3)
 
	
Step 1: Interrupt INCB050465 until the toxicity has resolved to <math>\leq</math> Grade 1.
 
Step 2: Restart INCB050465 at same dose. If assessed as related to INCB050465, restart at next lower dose.

 
• Exfoliative dermatitis (Grade 1)
 
	
Step 1: Interrupt INCB050465 until the toxicity has resolved.
 
Step 2: Restart INCB050465 at next lower dose. Monitor as clinically indicated.

 
• Exfoliative dermatitis (<math>\geq</math> Grade 2)
 
	Permanently discontinue INCB050465.

 
• Intestinal perforation (any grade)
 
	Permanently discontinue INCB050465.

 
• Pneumocystis jiroveci pneumonia infection
 
	Interrupt INCB050465. Permanently discontinue INCB050465 if Pneumocystis jiroveci pneumonia infection is confirmed.

 
• CMV infection
 
	Subjects with CMV viremia without associated clinical signs of CMV infection should be carefully monitored. Consider interrupting INCB050465 for subjects with CMV viremia and clinical signs of infection until the infection has resolved. Restart INCB050465 reduced by 1 dose level if approved by the medical monitor.

 
• Varicella zoster infection
 
	Interrupt INCB050465. Restart INCB050465 only by approval of the medical monitor.

 
• Any Grade 1 or Grade 2 toxicity unless otherwise specified.
 
	Continue study treatment and treat the toxicity; monitor as clinically indicated.

 
• Any Grade 3 toxicity, if clinically significant and not manageable by supportive care unless otherwise specified.
 
	
Step 1: Interrupt INCB050465 up to 14 days until the toxicity has resolved to <math>\leq</math> Grade 1.
 
Step 2: Restart INCB050465 at same dose. If assessed as related to INCB050465, restart at next lower dose. If interrupted for <math>></math> 14 days, contact the medical monitor for approval to restart INCB050465. Monitor as clinically indicated.

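### Table 2 has no platelet row for 25 to < 50 × 10⁹/L in subjects enrolled above 100 × 10⁹/L, so the written trigger for holding drug is weaker at 40 than at 60 or 20

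*Protocol*

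**What the plan says.** All platelet counts below are in units of 10⁹/L. Protocol Section 5.4.1, Table 2 (Hematology), has three platelet entries:

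- "Platelet count is Grade 2 (50 to" < 75), for subjects who enrolled above 100. Action: interrupt for up to 14 days until recovery to Grade 1 or better, or to the pretherapy level. Then: "Restart INCB050465 at same dose; monitor as clinically indicated".
- "Platelet count is Grade 3" (below 50), for subjects who enrolled at or below 100. Same action.
- "Platelet count is Grade 4" (below 25), for all subjects. Action: interrupt for up to 14 days until Grade 1 or better, then restart at the same dose, or at the next lower dose if the event is related.

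A Grade 3 event with no row of its own goes to the generic entry in the continued part of Table 2: "Any Grade 3 toxicity, if clinically significant and not manageable by supportive care unless otherwise specified". Its restart rule reads "If assessed as related to INCB050465, restart at next lower dose. If interrupted for" more than 14 days, "contact the medical monitor for approval to restart INCB050465".

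The text before the table adds: "Individual decisions regarding dose interruption and reduction should be made using clinical judgment", in consultation with the medical monitor. Inclusion criterion 7c admits subjects from a platelet count of 50 upward, so both entry strata can occur.

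**The concern.** A hold rule should not loosen as the count gets worse. Here the stratum with better entry counts gets the earlier trigger, a hold already at Grade 2, but loses its unconditional trigger at Grade 3 and regains it at Grade 4. A site that applies the table literally could keep dosing a subject at 40 because supportive care is coping, when the same table would have stopped drug at 60 without that test. At 40, a subject enrolled at 101 also has a weaker written trigger than one enrolled at 100. What is at stake is consistent handling of low platelets, not any efficacy estimate.

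**Working it through.** The plan states no figure to reproduce. The check is to take each count and find the Table 2 row that governs it, using the printed cut-offs as bounds.

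**Inputs.** The three platelet rows, the generic Grade 1 or 2 row and the generic Grade 3 row, all from Table 2. Example entry counts are 101 (just above the stratum limit) and 100 (at it).

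| Count on drug | Enrolled at 101 | Enrolled at 100 |
|---|---|---|
| 74, 60, 50 | Grade 2 platelet row: hold; restart same dose | Generic Grade 1 or 2 row: continue |
| 49, 40, 25 | Generic Grade 3 row: hold only if clinically significant and not manageable; lower dose if related | Grade 3 platelet row: hold; restart same dose |
| 24, 20 | Grade 4 platelet row: hold; lower dose if related | Grade 4 platelet row: hold; lower dose if related (the Grade 3 row's below-50 cut-off is also met) |

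Reading down the middle column, the trigger goes hold, conditional hold, hold. Reading down the right-hand column, it only tightens. The gap is exactly 25 to < 50 in subjects enrolled above 100.

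**Trigger and restart are separate.** Across the same three bands in the middle column, restart goes same dose, lower dose if related, lower dose if related. That sequence does not weaken. Only the trigger is inverted.

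**When the gap can be met.** A subject already held under the Grade 2 row stays off drug until Grade 1 or better, which begins at 75. The gap therefore matters mainly for a subject on drug (including one restarted after a Grade 2 hold) who goes from 75 or above to 25 to < 50 between two draws. The fall needed to reach 50 is:

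- from 75: (75 − 50) / 75 = 33.3%
- from an entry count of 101: (101 − 50) / 101 = 50.5%

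The actual fall must exceed these. Table 5 schedules hematology at Day 15 and every 3 weeks. For subjects continuing after Amendment 4, Table 7 lists it at least every 12 weeks, while Sections 7 and 7.4.5 leave frequency to standard of care.

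**After the fix.** For a subject enrolled at 101: 60 gives hold, same dose; 40 gives hold, lower dose if related; 20 gives hold, lower dose if related. Neither the hold nor the restart rule weakens as the count falls.

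**The case against.** **The Grade 2 row obviously means Grade 2 or worse.** Several Table 2 thresholds are one-sided (Grade 3 ANC, Grade 3 ALT/AST), and an investigator told to hold at 60 would surely hold at 40. The practical half of this stands and is a main reason the point is minor. The textual half does not: this row prints a lower limit of 50, and Table 2 marks a wider band where it wants one, as for diarrhea, pneumonitis, skin toxicity and exfoliative dermatitis.

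**Clinical judgment covers it.** Section 5.4.1 does make the table guidance, so a missed hold is unlikely. But that clause applies to every band equally and does not put the bands in order.

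**It may be deliberate.** No reason is given. The other Grade 3 laboratory triggers in Table 2 (ALT/AST, ANC, and platelets in the lower stratum) all call for interruption without this condition, apart from the note directing sites to the sponsor for liver metastasis-related elevations at baseline.

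**Stronger readings that the documents do not support.** A reader might infer that there is no instruction at 40; there is one, but it is conditional. A reader might infer that the table is more lenient overall at 40 than at 60; its restart rule is stricter. A reader might also take a frequency from Section 1.3, where no Grade 3 or worse treatment-related adverse event (AE) reached 10% of 46 Phase 1 subjects, hence at most 4 (4/46 = 8.7%; 5/46 = 10.9%). That statement concerns treatment-related AEs. Under Section 8.1.1 of this protocol an abnormal laboratory value is an AE only if it causes signs or symptoms, is clinically meaningful, needs therapy or changes study drug, and Phase 1's own definition is not given. An asymptomatic count of 40 left on drug, which is the case at issue, need not be counted, so Section 1.3 does not bound it.

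**Few subjects remain.** Amendment 4 reduces procedures for ongoing subjects, so a change now reaches only those still on drug. This limits the benefit.

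**Conclusion.** The gap is real and minor. As written, a subject enrolled above 100 has an unconditional hold at 50 to < 75, a conditional one at 25 to < 50 and an unconditional one below 25. At 25 to < 50 the trigger is also weaker than for a subject enrolled at or below 100. The inversion is confined to the interruption trigger.

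This rests on reading the printed limits as they stand. The number of subjects affected is unknown. Thrombocytopenia is not named among the common, serious or discontinuation-causing Phase 1 events in Section 1.3, nor among the events of special interest in Section 8.4. That is absence of a named signal, not evidence about how often Grade 3 counts occur. Objective response rate, duration of response, progression-free survival and overall survival analyses are unaffected.

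**What to change.** Add one entry to the Table 2 hematology block that already holds the Grade 4 platelet row: Grade 3 platelets, 25 to < 50 × 10⁹/L, in subjects whose entry count was above 100 × 10⁹/L. That block's action then applies: hold for up to 14 days until Grade 1 or better, then same dose, or next lower dose if related. Leave the other rows unchanged.

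This makes the hold unconditional and keeps the lower-dose-if-related restart that the generic row now gives. The new entry should not carry its own line on approval after 14 days. The Grade 4 row has none, so the new row would look stricter than Grade 4. Section 5.4.1 already requires contact with the sponsor before restarting after more than 14 days, and Section 5.5.1 requires discontinuation for a persistent AE delaying therapy beyond 14 days unless the sponsor approves.

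One difference stays as it is today: at 40, restart is at the same dose for a subject enrolled at or below 100, and at the lower dose if related for one enrolled above 100.

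The cost is one table entry in the next protocol amendment, approved by the sponsor and then the ethics committee under Section 10.1, with no new assessments.
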